12.0 CRITERIA FOR THERAPEUTIC RESPONSE/OUTCOME ASSESSMENT

12.1 Assessment of Primary Objective

The grading of skin toxicity will be based on the CTCAE version 4.0 scale as defined in section 3.4. To ensure unbiased skin toxicity measurement, both the clinical team and patient will be blinded to the treatment assignment. The type of skin toxicity (moist desquamation or grade ≥ 2 erythema), maximal score, its location within the target (chest wall or axilla), and time to occurrence will be recorded weekly during RT and at week 2 follow-up on the Provider Skin Toxicity Assessment Form. Following the post-treatment visit, the patient will not need to return to the clinic for other follow-up visits unless otherwise specified by the treating physician.

12.2 Assessment of Secondary Objectives

The Skindex-16 module score will be utilized to assess patient-reported toxicities at baseline, during week 5 of RT, and 10-14 days post-RT.

The maximal reported toxicity score and time to occurrence will be assessed weekly and at the two week follow up.

13.0 CRITERIA FOR REMOVAL FROM STUDY

It will be made clear to all participants that they are allowed to withdraw from the study at any time. If at any time the patient is found to be ineligible from the protocol as designated in the section on Criteria for Patient/Subject Eligibility, the patient will be removed from the study.

14.0 BIOSTATISTICS

This is a double-blinded, randomized trial (see Section 15.2 for details of randomization) to compare MF 0.1% cream with standard skin care (Eucerin) on the prevention of moderate to severe skin toxicities in breast cancer patients receiving post-mastectomy radiation to the chest wall and regional lymph nodes. A patient is deemed to have developed skin toxicity if she has a grade ≥ 2 skin toxicity as defined in Section 3.4 within 7 weeks from the beginning of radiation.

Based on estimates provided by radiation oncologists at our institution, the rate of grade ≥ 2 toxicity using Eucerin as skin care for chest wall radiation is $\approx 50\%$. This estimate is slightly lower than the findings from the Spierer study cited in section 3.2, to reflect this study's inclusion of patients treated with photons (in the presence of reconstruction) as well as electrons. We expect that the usage of MF can reduce this rate to 25%. 124 evaluable patients are needed for the comparison, with 62 patients in each arm. Two-sample, two-sided proportion tests will be used to derive the statistical significance. One interim analysis will be conducted when 31 patients in each arm have been enrolled and evaluated using the O'Brien-Flemming procedure, which will declare significance if the test p-value is less than 0.005. Correspondingly the final analysis will declare significance if the test p-value is less than 0.048. This design has a power of approximately 0.83 (i.e., detecting the true toxicity rate of 25% or lower) at the type I error (i.e., declaring MF more effective while it yields the same toxicity rate as Eucerin) rate of 0.05 based on 100000 statistical simulations.

All deaths unrelated to the toxicities, and patients lost to follow-up (before toxicities can be evaluated), will be excluded from the comparison and new patients will be accrued for replacement. To this end we plan to enroll an additional 15% of patients. Therefore our final proposed accrual is about 143 patients, which is expected to be done in 3 years.

Patient-reported skin symptoms will be scored from the Skindex-16 surveys and compared between interventions using Wilcoxon tests at each separate assessment time point. Analysis of covariance may also be used when the baseline information is taken into account as a covariate. Multiple comparison tools will be employed to adjust for statistical significance levels. Maximum reported skin toxicities will be tabulated and summary statistics will be provided. Time to occurrence of skin toxicity will be handled by routine survival analysis such as Kaplan-Meier estimation, log-rank tests, and/or Cox regression models when comparisons are needed.

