3.2 Radiation-Induced Dermatitis

A variety of patient and treatment-related factors such as fractionation schedules, dose, size of the treatment field, concurrent chemotherapy, use of bolus or other beam-modifying devices, and individual genetic variation can affect the intensity of the skin reaction to radiation (Tucker, Turesson et al. 1992). The majority of data available regarding side effects are generated from patients receiving radiation to the intact breast, not the chest wall after mastectomy. Side effects are generally categorized as acute if occurring during or within 6 weeks of radiation treatment and late if occurring >6 weeks after completion of treatment. A common acute toxicity is dermatitis within the irradiated volume. Typically, the skin becomes erythematous and/or hyperpigmented, and may desquamate, in particular in the area of skin folds such as the axilla, supraclavicular fossa, or inframammary fold. Desquamation may be dry or moist. Progressive erythema may be seen after 10-20 Gy, depending on the fractionation schedule (Turesson and Notter 1975), and reaches maximal intensity approximately 1-2 weeks following the completion of treatment. An example of the development of moist desquamation and grade 2 erythema in a woman 1 week post-completion of PMRT to an unreconstructed chest wall is illustrated in Appendix 3.

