Factors contributing to variation in the severity of dermatitis in patients receiving PMRT have not been well studied. Acute skin toxicities are generally more severe in the setting of PMRT than breast conservation therapy (BCT), as the skin itself is considered part of the radiation target with PMRT. There are remarkably little data available on the incidence of radiation dermatitis in the post-mastectomy chest wall setting. The three large randomized trials investigating the use of PMRT either do not report toxicity or report late toxicity excluding skin toxicities (Overgaard, Hansen et al. 1997; Overgaard, Jensen et al. 1999; Ragaz, Olivotto et al. 2005). One small retrospective series of 89 patients receiving PMRT using an electron technique reported that 19 patients developed dry desquamation, and only five developed moist desquamation (Hehr, Budach et al. 1999). In contrast, a series of 118 patients treated with a similar technique reported that 52% of patients developed grade 3-4 skin toxicity by Radiation Therapy Oncology Group (RTOG) criteria, and 31% of patients required an unplanned treatment break to recover from early radiation-induced skin toxicities (Spierer, Hong et al. 2004).

The development of normal tissue toxicities in breast cancer patients receiving adjuvant external beam RT demonstrates significant heterogeneity among individuals (Twardella, Popanda et al. 2003), which can be attributed to a variety of individual, tumor stage, cellular, and molecular factors. Increasing evidence suggests that individual genetic variations may also play a significant role in the development of adverse radiation responses (De Ruyck, Van Eijkeren et al.

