Bostrom et al, 2001	N=49, whole breast	Mometasone furoate 0.1% vs Placebo	MMF group with significantly decreased acute radiation dermatitis (P=0.0033).
Schmuth et al, 2002	N=36 ,whole breast	0.1% methylprednisolone cream vs 0.5% dexamethasone cream vs no intervention	No significant difference in mean severity scores of radiation dermatitis
Shukla et al, 2006	N=60, whole breast	Beclomethasone dipropionate spray vs no intervention	Corticosteroid group with significantly reduced incidence of moist desquamation
Omidvari et al, 2001	N=51, chest wall	Betamethasone 0.1% vs placebo vs no intervention	Steroid arm with significantly delayed occurrence of ARD
Miller et al, 2011	N=176; 140, whole breast; 29, chest wall	Mometasone Furoate 0.1% vs Placebo	No difference in the mean maximum grade of radiation dermatitis

Mometasone furoate is a medium-strength topical steroid that has a low atrophogenic potential, and has demonstrated greater anti-inflammatory activity and a longer duration of action than other medium-strength topical steroids such as betamethasone (Prakash & Benfield, 1998). MF has been shown to be effective in reducing clinically appreciated radiation dermatitis and pruritus in patients who are receiving whole breast radiotherapy in several randomized trials comparing MF with a placebo emollient (Bostrom, Lindman et al. 2001; Miller, Schwartz et al. 2011). However, its applicability in patients who have undergone mastectomy and receive irradiation of the chest wall has not been established. Only one of these studies included patients who received chest wall radiotherapy but, because the sample size was so small, they were unable to draw definitive conclusions regarding the benefit of MF in this population (Miller et al., 2011). The aim of this study is to elucidate the effect of mometasone furoate versus standard of care on patients receiving post-mastectomy irradiation, specifically.

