The topical agents will be blinded and dispensed after randomization at patient's simulation visit or at the radiation setup in 130 gram jars labelled with patient's name and MRN by the Memorial Sloan-Kettering Cancer Center (MSKCC) pharmacy. It is estimated that the average patient will require approximately 3 grams of cream per application, and will require one additional prescription for a jar of study cream during the 7 week trial. During weekly assessment of compliance at routine status check, date of dispensation of second jar will be recorded on provider assessment sheet as an additional indicator of compliance.

Patients will return to clinic for a follow up visit at 10-14 days following the completion of RT. At this visit the study investigator will perform a skin assessment and the patient will complete the Skindex-16.

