9.2 Chest Wall Radiotherapy

The radiation treatment included in this study represents the institutional standard of care and is not influenced by the patient's decision to participate in this study. Either photons or electrons will be used for the primary radiotherapy treatment, depending on reconstruction status of the patient. Patients without reconstruction receive electrons directed en face to

the chest wall with customized bolus, or photon tangents with daily bolus over the chest wall. Patients who have a reconstruction are treated with two tangential photon beams and bolus over the reconstructed breast everyday. Treatment breaks necessitated by severe toxicities will be recorded and will not be considered deviations.

Concurrent delivery of chemotherapy will not be allowed. Biologic agents and hormonal therapy during radiation will be permitted.

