10.2 Evaluations After Radiation

Follow-up visits will be completed 10-14 days after the completion of RT. At this time, provider assessment of skin toxicity will be performed by the physician and RN, and the patient will complete another Skindex-16 form.

Tests and Observations	Consultation	Simulation	Set-Up/ Treatment #1	During Treatment (5 weeks)	10-14 Days Following Completion of Treatment (CoT)
History and Physical	X			Weekly Status checks	
Radiation Treatment Plan approval		X			
Randomization		X			
Patient Teaching and Administration of Topical Agent		X	X	Assess compliance weekly	
Provider Assessment of Skin Toxicity		X		Provider assessment weekly	X
Patient Assessment of Fitzpatrick Category (Appendix 2)		X			
Patient Assessment of Skin Toxicity (Appendix 1)		X		Week 5 only	X

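### The primary endpoint window runs 7 weeks from the start of radiation, but the last skin check is timed from its end, so after two or more lost treatment days that check can fall outside the window

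*Combined protocol and SAP*

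**What the plan says.** Section 14 gives the only rule for who counts as having the primary event: grade 2 or higher skin toxicity "as defined in Section 3.4 within 7 weeks from the beginning of radiation". The clock starts at the first fraction.

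The last provider skin assessment uses a different clock. Section 10.2 states: "Follow-up visits will be completed 10-14 days after the completion of RT". Section 12.1, under the heading for the primary objective, lists that visit as a recording point: toxicity type, maximal score, location and "time to occurrence will be recorded weekly during RT and at week 2 follow-up on the Provider Skin Toxicity Assessment Form".

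Section 3.2 says that erythema "reaches maximal intensity approximately 1-2 weeks following the completion of treatment", which is about when this visit takes place. Section 9.1 says the average patient "will require one additional prescription for a jar of study cream during the 7 week trial", which suggests that 7 weeks is the nominal 5 weeks of radiation plus 2 weeks of follow-up.

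On interruptions, Section 9.2 says: "Treatment breaks necessitated by severe toxicities will be recorded and will not be considered deviations". Section 11 does not anticipate breaks for severe skin toxicity or cellulitis. No section extends the 7-week limit when treatment is prolonged, or says how a post-radiation visit after day 49 is scored.

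**The concern.** The visit is the only scheduled look at the skin after radiation, and it is timed close to the expected peak. If treatment runs long, the visit moves later and the window does not. A patient with new grade 2 dermatitis at a visit held exactly on schedule could then be scored as event-free in the primary test. The same reaction would still enter the Section 12.2 summaries of maximal toxicity and time to occurrence, which carry no 7-week limit.

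There are two alternative consequences. If timing is the same in both arms, true events are lost from both and some power goes. If MF delays reactions relative to Eucerin, proportionately more MF events are lost and the comparison tilts towards MF. If the rule is not settled in advance, the scoring of late visits falls to the analyst, possibly after outcomes are known.

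**Working it through.** **Inputs.** From the documents: 5 weeks and 50 Gy (Section 1.0 schema); visit 10-14 days after completion (Section 10.2); window 7 weeks = 49 days, 62 per arm, 50% against 25%, interim p < 0.005 at 31 per arm, final p < 0.048, power about 0.83 (all Section 14). Assumed: 25 weekday fractions, each lost weekday made up at the end, first fraction on day 0, visits on weekdays. The rate of lost days and the share of events first seen at the visit are not in the documents and are varied below.

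**1. The plan's power.** Exact binomial enumeration of the two-look design (pooled z test, no continuity correction) gives 0.835, matching the stated figure of about 0.83. The later steps use the final look only, which gives 0.834.

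**2. Calendar.** Visit range = day of last fraction + 10 to + 14, for each start weekday. The share outside is the share of permitted weekday slots after day 49, averaged over the five start weekdays.

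| Lost days | Last fraction (day) | Visit range (day) | Share outside, slots spread evenly | Share outside, earliest slot |
|---|---|---|---|---|
| 0 | 32 or 34 | 42-48 | 0% | 0% |
| 1 | 35 | 45-49 | 0% | 0% |
| 2 | 36 or 38 | 46-52 | 29% | 0% |
| 3 | 37 or 39 | 47-53 | 58% | 0% |
| 4 | 38 or 40 | 48-54 | 87% | 60% |
| 5 | 39 or 41 | 49-55 | 96% | 80% |
| 6 | 42 | 52-56 | 100% | 100% |

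With two lost days only the late end of the range is outside: day 14 after radiation for Monday to Thursday starts, days 12-14 for a Friday start. If the first fraction is called day 1 and the window closes on day 49 of that count, one lost day is enough.

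**3. How many visits are late.** Lost days taken as Poisson, applied to 124 patients:

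| Assumed mean lost days | Late, slots spread evenly | Late, earliest slot |
|---|---|---|
| 0.5 | 3% (4) | 0.1% (0) |
| 1 | 11% (13) | 1% (2) |
| 2 | 31% (39) | 10% (12) |

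**4. Effect on the test.** Let f be the share of late visits and s the share of events first seen at the visit. If every such event at a late visit is lost, the observed rate = p × (1 − f × s). Exact enumeration, 62 per arm, pooled two-sided z test at 0.048.

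*Equal timing, s = 20% in both arms, 50% against 25%.* At f = 10% the observed rates are 0.50 × 0.98 = 0.490 and 0.25 × 0.98 = 0.245. The expected loss is 62 × 0.50 × 0.10 × 0.20 = 0.6 Eucerin events and 62 × 0.25 × 0.10 × 0.20 = 0.3 MF events. Power goes from 0.834 to 0.830 (f = 3%), 0.820 (10%) or 0.791 (31%). The chance of falsely declaring MF better stays at 0.027.

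*Unequal timing, s = 20% Eucerin and 40% MF.* With a true 50% in both arms and f = 10%, the observed rates are 0.50 × 0.98 = 0.490 and 0.50 × 0.96 = 0.480. The chance of a significant result in favour of MF goes from 0.027 to 0.029 (f = 3%), 0.034 (10%) or 0.057 (31%). For a true 50% against 25%, power is 0.834, 0.836 and 0.845, so nothing is lost.

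**The case against.** The strongest reply is that the intent is plain. Section 12.1 assigns the visit to the primary objective and Section 9.1 describes a 7-week trial, so harm requires an analyst to treat a nominal length as a hard cut-off. That stands as evidence of intent. A reader might infer that the plan means to exclude the post-radiation visit; the documents do not support that. But Section 14 is the operative rule and contains no exception, so the intent should be written there.

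Second, Section 14 asks whether she has the toxicity within 7 weeks, not whether she is examined within 7 weeks. A reaction seen on day 50 may have begun earlier, and time to occurrence is recorded. This also stands, and it makes the figures above an upper bound for each scenario.

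Third, a reader might take the cited electron series, in which "31% of patients required an unplanned treatment break to recover from early radiation-induced skin toxicities", as the share of late visits here. It is not. Those breaks were for skin toxicity, so most such patients would already have a recorded event, and Section 11 does not anticipate breaks of that kind. The 31% late visits in the working comes from an assumed mean of two lost days with evenly spread visits; that the two percentages match is coincidence.

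Fourth, a reader might infer that the rule favours MF. Table 2 does report "Steroid arm with significantly delayed occurrence of ARD", in chest wall patients, but for betamethasone and for any acute radiation dermatitis. Later onset at grade 2 or higher with MF is an assumption.

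**Conclusion.** The mismatch is real: read literally, Section 14 can score a grade 2 reaction found at a correctly scheduled visit as no event. It cannot happen in an uninterrupted 5-week course. It becomes possible from two lost treatment days, assuming 25 weekday fractions. The exposure is mainly patients still below grade 2 who lose days for reasons other than skin toxicity, and the documents give no rate for this.

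The effect is probably small. At 3-10% late visits it is either a power loss of at most 0.834 − 0.820 = 0.014 with equal timing, or a rise of at most 0.034 − 0.027 = 0.007 in the chance of falsely declaring MF better with the assumed 40% against 20% timing. These are alternatives and should not be added together. The larger figures (power 0.791, false-positive chance 0.057) need a mean of two lost days per patient and visits spread evenly over days 10-14; booking on the earliest permitted weekday brings the same mean back to 10% late. The point is worth correcting because it touches the primary endpoint and costs almost nothing to settle, not because it threatens the trial's conclusion.

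**What to change.** In Section 14, define the primary endpoint as any CTCAE grade 2 or higher skin toxicity from the first fraction through the scheduled 10-14 day post-radiation visit, whatever day that visit falls on counted from the start of radiation. Keep the 7-week version as a sensitivity analysis, and record the dates of the first and last fraction and of the visit so that both can be computed. Make the change before the interim look at 31 per arm.

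If a grace period for late visits is wanted, keep it short and justify it: study cream stops 10-14 days after radiation, so a much later assessment would be off treatment and past the expected peak.

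The cost is an amendment to the endpoint wording. No visits or patients are added, and the sample size and stated power do not change. The downside is that time at risk from the first fraction varies by a few days between patients, although each is assessed at a comparable point after radiation.

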1.0 PROTOCOL SUMMARY AND/OR SCHEMA

This is a double-blinded, randomized trial. Its purpose is to compare the steroid cream mometasone furoate 0.1% (MF), with standard emollient skin care, Eucerin, on the prevention of grade 2 or higher skin toxicities in breast cancer patients receiving PMRT to the chest wall and regional lymph nodes. Patients will be stratified based on two variables: the presence of a reconstruction in order to achieve a balanced population of patients being treated with either photon or electron beams, and body mass index (BMI <30 vs ≥30).

Female breast cancer patients who have received mastectomy + axillary surgery and will undergo postmastectomy radiation (PMRT) at our institution are eligible for this study. Enrollment of 143 patients is expected to take place over 3 years.

Skin toxicities using the Common Terminology Criteria for Adverse Events (CTCAE) v.4 scale will be scored by evaluating RN or MD . Assessments will be completed at baseline, weekly during radiation therapy (RT), and 10-14 days following the completion of RT. Patient-reported skin symptoms will also be assessed at baseline, at week 5 of RT, and 10-14 days following completion of RT.

Screening	Randomization	Pre-RT	Weekly During RT (5 weeks, 50 Gy)	Follow-up (10-14 Days Post-RT)
143 breast cancer patients status post mastectomy + axillary surgery, ± chemotherapy 
 Stratifications: 
 Reconstruction Yes vs no Body Mass Index <30 vs ≥30 	Eucerin BID 
 or mometasone furoate 0.1% BID 	
 Baseline H and P Baseline Provider Skin Toxicity Assessment Baseline Skindex-16 questionnaire Patient education on topical cream usage 	
 Weekly status checks Weekly skin cream compliance assessed Provider Skin Toxicity Assessment Skindex-16 questionnaire during Week 5 of RT 	
 Skin cream compliance assessed Provider Skin Toxicity Assessment Skindex-16 questionnaire

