8.0 PRETREATMENT EVALUATION

The History and physical exam in Radiation Oncology will include information on race/ethnicity, age, body mass index, chemotherapy status, hormone therapy, smoking history/status, diabetes, high blood pressure, Eastern Cooperative Oncology Group (ECOG) performance, and reconstruction status.

Radiation Treatment Planning will be approved by the treating MD, in order to determine type of chest wall radiotherapy (photons vs electrons) to be administered, as outlined in section 9.1.

Baseline Provider Skin Toxicity Assessment will be done within 14 days prior to the start of RT.

Patients will complete a baseline Skindex-16 Questionnaire and Fitzpatrick Skin Classification within 14 days prior to the start of RT (Appendix 1 and 2).

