15.2 Randomization

Randomization will be done at MSKCC. Patients will be randomized to the MF 0.1% cream arm or the standard skin care arm with Eucerin at the ratio of 1:1. For patients enrolled at MSKCC, after eligibility is established and immediately after consent is obtained, the RSA will register participants in the PPR system and randomize participants using the Clinical Research Database (CRDB), by calling the MSKCC PPR Office at [contact] between the hours of 8:30 am and 5:30 pm, Monday to Friday. Randomization will be accomplished by the method of random permuted block, and will be stratified by the presence of breast reconstruction and BMI. After treatment arm is determined by randomization, RSAs at MSKCC will notify the research staff of the participant ID via email within 24 hours of randomization. Since this is a double blind study, the research participants' treatment assignments can be viewed in the CRDB only by the hospital pharmacists who are dispensing the study drugs.

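### The primary test ignores the reconstruction and BMI strata used to randomise; a stratified test costs almost nothing and gains power if the strata are strongly prognostic.

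*Combined protocol and SAP*

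**What the plan says.** Section 1.0 announces the stratification: "Patients will be stratified based on two variables: the presence of a reconstruction", with BMI below 30 versus 30 or above as the second factor. Its reason for the first factor is balance by beam type: "the presence of a reconstruction in order to achieve a balanced population of patients being treated with either photon or electron beams". Section 15.2 gives the mechanism: "Randomization will be accomplished by the method of random permuted block, and will be stratified by the presence of breast reconstruction and BMI". Two binary factors make four strata.

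Section 14.0 gives the primary analysis in one sentence: "Two-sample, two-sided proportion tests will be used to derive the statistical significance". It applies at an interim look with 31 patients per arm (p < 0.005) and at the final look with 62 per arm (p < 0.048). Covariates appear in Section 14.0 only for secondary endpoints. For the Skindex-16 scores: "Analysis of covariance may also be used when the baseline information is taken into account as a covariate". Cox regression is mentioned only for time to occurrence. Section 8.0 lists both stratification factors among the pretreatment data: "body mass index, chemotherapy status, hormone therapy, smoking history/status, diabetes, high blood pressure, Eastern Cooperative Oncology Group (ECOG) performance, and reconstruction status".

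**The concern.** Blocking within strata removes from the treatment comparison whatever variation in dermatitis risk the strata explain. A pooled test does not know this. Its standard error still contains the between-stratum variation, so it is too large when the strata predict the outcome. The test then rejects too rarely under the null and gives up some power under the alternative.

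The protocol itself suggests that reconstruction may matter: Section 14.0 sets the control rate a little below that of a published electron series because reconstructed patients treated with photons are included. If reconstruction and BMI are strongly prognostic, the trial stratifies on them but does not collect the precision this makes available. An adjusted analysis requested later would also be post hoc, because none is pre-specified.

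**Working it through.** **Inputs from the documents.** Section 14.0: control rate about 50%, MF rate 25%, 62 evaluable patients per arm, looks at 31 and 62 per arm, two-sided cut-offs 0.005 and 0.048, stated power about 0.83, type I error 0.05. Section 15.2: 1:1 allocation, permuted blocks within reconstruction × BMI.

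**Inputs assumed, because the documents give none.** 50% reconstructed and 30% with BMI ≥ 30 (alternative: 70% and 25%); odds ratios (OR) of 1 to 4 for the effect of each factor on dermatitis; a common treatment odds ratio across strata; blocks of 4.

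**Step 1: the plan's own figure.** For a single look,

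power = Φ{ [δ√n − z√(2p̄(1−p̄))] / √(p₀(1−p₀) + p₁(1−p₁)) }

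with δ = 0.25, n = 62 and p̄ = 0.375:

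- α = 0.05: (0.25 × 7.874 − 1.960 × 0.6847) / 0.6614 = 0.947, so power is 0.828.
- α = 0.048 (z = 1.977): power is 0.824.
- Both looks, exact enumeration of the uncorrected pooled test: 0.835.

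The stated 0.83 is reproduced. The two cut-offs give an overall normal-theory α of 0.0499.

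**Step 2: why the plain test is conservative.** Take both factors at OR 3 in the base case. Control rates that average 50% are 29.5% (35% of patients), 55.7% (the two middle strata, 35% + 15%) and 79.0% (15%). The within-stratum variance is

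0.35 × 0.295 × 0.705 + 0.50 × 0.557 × 0.443 + 0.15 × 0.790 × 0.210 = 0.221.

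The plain test uses 0.50 × 0.50 = 0.25. The true standard error is therefore about √(0.221/0.25) = 0.940 of the one used. The nominal critical value 1.977 acts as 1.977/0.940 = 2.10, which is a two-sided level of about 0.035 at the final look instead of 0.048. Simulation of the final look alone gave 0.037.

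**Step 3: plain test against CMH.** The CMH statistic without continuity correction is

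z = |Σ(aₛ − n₁ₛtₛ/nₛ)| / √Σ[n₁ₛn₀ₛtₛ(nₛ − tₛ) / (nₛ²(nₛ − 1))]

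where, in stratum s, aₛ is MF events, tₛ all events, n₁ₛ and n₀ₛ the arm sizes, and nₛ their sum. Each scenario used 100,000 simulated trials with both looks (Monte Carlo SE about 0.001 for power, 0.0007 for type I error). Marginal rates were held at 50% versus 25%. In the OR 3 example the MF rates are 10.8, 26.7, 26.7 and 52.3%.

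Base case (50% reconstructed, 30% BMI ≥ 30):

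| Stratum effect | Power, plain | Power, CMH | Type I, plain | Type I, CMH |
|---|---|---|---|---|
| None | 0.832 | 0.827 | 0.0525 | 0.049 |
| Both OR 1.5 | 0.836 | 0.835 | 0.050 | 0.050 |
| Both OR 2 | 0.837 | 0.844 | 0.047 | 0.051 |
| Reconstruction only, OR 3 | 0.840 | 0.851 | 0.043 | 0.049 |
| BMI only, OR 3 | 0.838 | 0.847 | 0.046 | 0.051 |
| Both OR 3 | 0.846 | 0.867 | 0.038 | 0.049 |
| Both OR 4 | 0.851 | 0.884 | 0.034 | 0.051 |

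With 70% reconstructed and 25% BMI ≥ 30, power (plain / CMH) is 0.832 / 0.827 with no effect, 0.837 / 0.842 at OR 2 and 0.845 / 0.864 at OR 3. A repeat simulation agreed to within about 0.003.

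**Step 4: sparse strata.** In the 70%/25% case the smallest stratum is 0.30 × 0.25 = 7.5% of patients: about 5 of 62 at the interim and 9 of 124 at the end. CMH type I error stays at 0.048 to 0.050.

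**The case against.** The strongest reply is that nothing is broken. The plain test is valid, it matches the power calculation, and stratified randomisation delivers the beam-type balance that Section 1.0 asks for without a stratified test. All of that stands, and it is why this is a suggested improvement only.

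The second argument is that the documents point to weak strata. Section 14.0 calls its 50% control rate only slightly lower than the electron series, which reported 52% (Section 3.2). If unreconstructed patients have 52% and half the patients are reconstructed, the reconstructed rate must be 48%, an OR of (0.52/0.48)/(0.48/0.52) = 1.17. With 70% or 30% reconstructed it is 1.12 or 1.31. With reconstruction at OR 1.17, power (plain / CMH) is 0.830 / 0.825 at BMI OR 1, 0.833 / 0.830 at 1.5, 0.833 / 0.834 at 2 and 0.840 / 0.848 at 3. On that reading CMH loses slightly or ties until BMI alone passes about OR 2. The arithmetic is right, but the premise is thin: 52% is RTOG grade 3-4 and 50% is a clinician estimate of CTCAE grade 2 or higher. The contrast cannot establish a weak effect, although nothing in the documents establishes a strong one either. Section 3.2 itself says that the determinants of severity in this setting are poorly studied, and Section 9.2 allows photons for unreconstructed patients, so reconstruction is an imperfect marker of beam type.

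Finally, every scenario assumes a common treatment odds ratio, which suits CMH. Differing treatment effects across strata were not examined. That limitation stands.

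**Conclusion.** The mismatch between design and analysis is real, and its consequence is modest. The plain test keeps its stated power and does not inflate type I error through the stratification; a positive result from it would be valid. Moving to a four-stratum CMH test costs about 0.5 to 0.6 points of power if the strata are not prognostic. It changes power by less than one point at OR 2 or below, gains about one point if one factor alone has OR 3, and gains 1.9 to 3.3 points if both have OR 3 to 4. In the strong-effect cases it also brings type I error from 0.034-0.038 back to about 0.05. These sizes rest on assumed stratum shares, block size, stratum effects and a common treatment odds ratio. The change is worth making because its possible loss is smaller than its possible gain and it needs no extra patients. Confidence is medium, because the strength of the strata is unknown.

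**What to change.** In Section 14.0, before the interim look:

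- Make the primary test, at both looks, a CMH test without continuity correction, stratified by the four randomisation strata (reconstruction yes/no × BMI < 30/≥ 30), at the existing 0.005 and 0.048 cut-offs.
- Report the stratified risk difference with a confidence interval.
- Keep the uncorrected two-sample proportion test as a sensitivity analysis.

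This also settles a point that Section 14.0 leaves open. With a continuity correction the plain test has simulated power of only 0.783, so the stated 0.83 implies an uncorrected test.

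The cost is one or two sentences. Both factors are recorded before treatment (Section 8.0) and already used to randomise. The sample size of 124 evaluable patients does not change. The only statistical cost is the half point or so of power if neither factor predicts dermatitis (0.832 to 0.827).
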